5.0 Adherence

It is recognized that there is a significant pill burden (15 capsules daily) for this study. Therefore, an effort will be made to measure adherence to the medication regimen in order to assist with the efficacy analysis and provide information that will be helpful if a phase III study is planned.

Adherence Measures

Procedures

Patient Education and Adherence Program

The adherence program for the study will consist of three central components: (a) informationalexchange, (b) skills development, and (c) social support enlistment. One of the tools utilized in this study will be the Medication Adherence Training Interview (i.e., MATI), a structured interview for medication education and adherence training. The MATI has been empirically tested in behavioral medical research in an HIV population and now has been modified for use in patients with chronic hepatitis C. The MATI will be reviewed by study coordinators and used as guidelines for on-going education and addressing medication adherence.

Baseline (day 0).

During this visit the study coordinator will also engage the participant in goal setting. Participants will be asked by the coordinator to set short-term goals (e.g., achieving a near-perfect adherence rate for the next 30 days) that may be important to the efficacy and safety of silymarin therapy. Participants will also be asked to create self-incentives for attaining the stated goals. The rationale is that individuals achieve greater self-directed change if they reward their successful efforts than if they provide no incentives for themselves.

Participants will be given a diary and asked to record the time of day they ingest each dose of study medication. The coordinator will assist the participant with planning a dosing schedule and integrating the medication times into lifestyle patterns. Participants will be encouraged to keep the portable diaries with them at all times or wherever they store their medications in their home or office. Participants will also be asked to track the number of alcoholic beverages consumed

on a daily basis. Participants will be encouraged to create a habit of completing the diary on a daily basis, preferably at the time of ingestion.

Study Visits. At subsequent study visits, participants will be asked about tolerance to medications and adherence will be stressed. The participant diary will be reviewed thoroughly and used as a tool to facilitate a discussion about adherence. Coordinators will apply strategies outlined in the original MATI to reinforce adherent behavior, and help participants problem-solve areas that need improvement. The tone of the discussion will be supportive and non-judgmental, while assisting the participant in identifying strategies to improve medication adherence. Coordinators will also review daily alcohol consumption and make recommendations when indicated.

Medication Adherence Outcomes

Primary: Cup counts. Patients will be asked to return all full cups to the coordinators. Missed doses (# of full cups returned) will be counted at each study visit.

Secondary: Patient self-report of missed doses in diaries. Patients will record the time of day for each dose ingestion in diaries. Study coordinators will record the number of self-reported missed doses on a monthly basis. In addition, silymarin levels measured at the specified visits will be used to identify non-adherent patients.

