2.3 Endpoints

Efficacy: The primary outcome variable (endpoint) for efficacy is whether or not serum ALT (mg/dl) is \leq 45 IU/L (approximate normal range) or achieves at least 50% decline to less than 65 IU/L (approximately 1.5 times the upper limit of normal) at the end of the 24-week treatment period. The relationship between dose and change in log₁₀(ALT) will also be investigated as a part of secondary analysis plans.

Safety: The primary outcome variable for safety is the occurrence of a dose-limiting toxicity during the 24-week treatment period. All adverse events (AE) will be categorized by severity.

Adherence: Will be measured using a summary of missed dose information obtained from patient diaries and dose counts and will be analyzed as both an outcome and as an explanatory variable in exploratory analyses of pharmacokinetic exposure and response.

Biomarkers: The following relationships will be explored: dose and change in biomarkers, changes in biomarkers and rate of treatment success, changes in biomarkers and rate of toxicity.

Rationale for using serum ALT and not liver biopsy as an endpoint:

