3.4.3 Dose-Specific Reduction Guidelines

AE Grade	Reduction?	Discontinue?	Silymarin	Placebo	Pill Burden
Mild	No	No	5	0	5
Moderate*	Yes	No	4	1	5
Severe**	Yes	Temp	3	2	5
Life Threatening	No	Yes	0	0	0

Dose Reduction Guideline – Silymarin 700 mg dose level

Dose Reduction Guideline – Silymarin 420 mg dose level

AE Grade	Reduction?	Discontinue?	Silymarin	Placebo	Pill Burden
Mild	No	No	3	2	5
Moderate*	Yes	No	2	3	5
Severe**	Yes	Temp	1	4	5

Life Inreatening No Yes 0 0 0

*Moderate AE: Patient can resume original dose level if AE improves or resolves. NOTE: If the subject experiences a drug related AE and two dose reductions are not tolerated, the subject will stop the drug

**Severe AE: Discontinuation for 1 week. If SAE improves or resolves, restart at indicated dose level at the investigator's discretion. The dose level may be increased to original dose level at the discretion of the investigator with continued close monitoring.

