6.2 Efficacy analysis

To address the primary objective 2, for each arm of the study, an estimate of the response rate π will be tabulated along with a corresponding 95% confidence interval. Point and interval estimates of mean change in log₁₀ (ALT) (a normalizing transformation) will also be tabulated.

The primary null hypothesis, H_{o1} : $\pi_o = \pi_{420} = \pi_{700}$, will be tested against the general alternative hypothesis, H_{a1} that response differs in at least one treatment arm via a chi-square test for association with $\alpha = 0.05$. If H_{o1} is rejected, then pair wise comparisons of the arms will be examined using a sequentially rejective test procedure (Holm, 1979).

Computation of these results for the intent to treat (ITT) analysis will comprise the main results of this study. Similar results will also be examined for the compliant-per-protocol subgroup of participants, defined as patients taking at least 80% of the medication.

Secondary analyses of efficacy will include model-based analyses of the relationship between dose and change in $log_{10}(ALT)$. Appropriate statistical models will be used in which change in $log_{10}(ALT)$ is the dependent variable. Study personnel will also perform analyses designed to aid interpretation of the main results or designed to be exploratory for purposes of hypothesis generation. For example, study personnel will use logistic regression models to investigate the relationship of pharmacokinetic exposure to treatment response.

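### The primary adherence measure counts only full cups brought back, so unreturned and part-used cups score as taken, and an 80% per-protocol set built on it can include patients who took well under 80%

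*Protocol*

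**What the plan says.** Protocol section 5.0 (Medication Adherence Outcomes) names cup counts as the primary measure. Patients are told what to bring: "Patients will be asked to return all full cups to the coordinators". The scoring rule follows: "Missed doses (# of full cups returned) will be counted at each study visit". Nothing is said about empty, part-used or missing cups.

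The same section adds two checks. The diary is the secondary measure: "Study coordinators will record the number of self-reported missed doses on a monthly basis". Blood concentrations form the other check: "silymarin levels measured at the specified visits will be used to identify non-adherent patients". Section 2.3 (Endpoints) combines the first two sources; its adherence entry reads: "Will be measured using a summary of missed dose information obtained from patient diaries and dose counts".

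Section 6.2 defines the compliant per-protocol subgroup only as "defined as patients taking at least 80% of the medication". It names neither the measure nor the denominator. It also says which analysis leads: "Computation of these results for the intent to treat (ITT) analysis will comprise the main results of this study".

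Section 3.4.3 keeps every dose at 5 capsules after a reduction by replacing silymarin capsules with placebo, for example in the table headed "Dose Reduction Guideline – Silymarin 420 mg dose level".

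**The concern.** A count of missed doses is only as good as the accounting behind it. Here the only evidence of a missed dose is a physical full cup, and no other cup is requested. Supply dispensed therefore cannot be reconciled with supply returned. Anything not seen is credited as taken, and a partly taken dose is credited in full.

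This matters because the protocol relies on adherence data. Section 3.4 fixes the pill burden partly so that compliance can be estimated. Section 5.0 acknowledges a heavy burden of 15 capsules a day and wants adherence data to help read the efficacy results and to inform a phase III trial. Section 2.3 uses adherence both as an outcome and as an explanatory variable in exploratory work. If the intent-to-treat result is null, readers will look to the per-protocol result to learn whether silymarin failed or was not taken. Inflated adherence blurs that answer.

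**Working it through.** The protocol gives no adherence figure to reproduce. Its only number here is the 80% cut-off, so the check applies the section 5.0 rule directly. One cup is taken to hold one 5-capsule dose, which is what equating full cups with missed doses implies.

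**Inputs.** 5 capsules per dose, three times daily, for 24 weeks (section 4.3); 80% cut-off (section 6.2); capsule numbers after reduction (section 3.4.3).

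**Planned doses.** 3 × 7 × 24 = 504. The cut-off is 0.80 × 504 = 403.2, so at least 404 doses must be taken and at most 100 missed.

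**Unreturned cups.** Let m be the share of doses missed and r the share of those full cups that come back. The rule gives a score of 1 − m × r, while true adherence is 1 − m.

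| Missed (m) | True adherence | r = 1 | r = 0.5 | r = 0.25 | r = 0 |
|---|---|---|---|---|---|
| 30% | 70% | 70% | 85% | 92.5% | 100% |
| 40% | 60% | 60% | 80% | 90% | 100% |
| 50% | 50% | 50% | 75% | 87.5% | 100% |

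The patient fails the cut-off only if m × r exceeds 0.20. At m = 40%, more than half of the full cups must come back before the patient is excluded.

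**Part-used cups.** Taking 3 of 5 capsules from every cup is 3/5 = 60% of capsules. No cup is full, so missed doses are 0 and the score is 100%.

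**Dose reductions.** A cup count cannot show these, because the cup still holds 5 capsules. While reduced, the share of assigned silymarin is:

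- 700 mg arm: 4/5 = 80% (moderate) or 3/5 = 60% (severe)
- 420 mg arm: 2/3 = 66.7% (moderate) or 1/3 = 33.3% (severe)

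These shares apply only during the reduction. If it starts at week w, is never reversed, and leaves a share f, the 24-week share is [w + f(24 − w)]/24. Ignoring any interruption, this falls below 80% when w is less than 24(0.8 − f)/(1 − f):

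- 700 mg severe: 24 × 0.2/0.4 = week 12
- 420 mg moderate: 24 × 0.1333/0.3333 = week 9.6
- 420 mg severe: 24 × 0.4667/0.6667 = week 16.8
- 700 mg moderate: never below 80%

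An example shows how far silymarin received and cup score can separate. A 420 mg patient has a severe event at week 4, one week off, then 1 silymarin capsule per dose for the remaining 19 weeks. Silymarin received is (3 × 4 + 1 × 19)/(3 × 24) = 31/72 = 43.1% of assigned. If the 21 cups of the interruption week come back, the cup score is (504 − 21)/504 = 95.8%.

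**The case against.** The strongest reply is that the cup count is not the whole measure. Section 2.3 uses diaries as well as dose counts, section 5.0 has the diary reviewed at visits, and silymarin levels are a further check. A completed diary would reveal unreturned cups and early stopping. This stands: a reader might infer that the protocol recognises only full cups, and it does not. But the diary is secondary, self-reported and kept by dose, so it need not show a part-taken cup. No rule says which source prevails. Levels are samples at visits, and a placebo patient has no study silymarin to detect whether or not capsules are taken.

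Second, section 6.2 does not tie 80% to the cup count, and a statistical analysis plan not seen here may define measure and denominator. This also stands, so the claim is that the set can include poor adherers, not that it will. A later plan could choose a denominator, but it could not recover cups that patients were never asked to return.

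Third, a reader might infer that anyone who stops at week 16 and returns nothing took 16 × 21 = 336 of 504 doses (67%) yet scores 100%. That holds only for an unrecorded stop. Section 3.5 provides an end-of-treatment visit after discontinuation, section 6.0 describes drop-outs, and nothing credits doses after a recorded stop.

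Fourth, a reader might infer that dose-reduced patients are wrongly classed as compliant. The documents do not support that. They follow a permitted schedule, some reductions leave 80% or more of assigned silymarin, and return to the original level is allowed. What is missing is a meaning for the medication in the 80% rule.

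Finally, it is tempting to say that the least adherent patients are the most often misclassified. That is plausible, since returning cups is itself adherent behaviour, but the protocol has no data on it.

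**Conclusion.** The point holds for the primary adherence measure. As written, the section 5.0 rule scores unreturned and part-used cups as taken, and both gaps move adherence upwards only. A patient at 60% true adherence can score anywhere from 60% to 100%, depending on what comes back or how capsules were skipped. An 80% per-protocol set based on cup counts can therefore include patients well below 80%.

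This assumes one dose per cup, the section 5.0 rule applied literally, and the per-protocol set drawn from cup counts, which is natural for the primary measure but not stated. How many patients would be affected cannot be derived from the protocol.

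The reach is limited to the supportive per-protocol analysis and the exploratory adherence analyses. The intent-to-treat result does not depend on it. The change is worth making before data collection because it concerns what is collected, but it does not threaten the main conclusion.

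**What to change.** - In section 5.0, ask patients to return all cups: full, part-used and empty. Count capsules, and reconcile the count with capsules dispensed, the diary and any recorded stop date.
- In section 6.2, define the 80% as capsules taken divided by capsules planned over 24 weeks, identically in all three arms. Count unaccounted capsules as not taken, with a sensitivity analysis counting them as taken.
- State that silymarin levels are not used to define the per-protocol set, since they would apply a different standard to placebo.
- Report silymarin received as a share of that assigned, separately and descriptively, without treating protocol-permitted reductions as non-compliance.

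The cost is some extra returning by patients and counting by coordinators who already handle cups at each visit, plus changes to the accountability form and analysis wording. The per-protocol set may become smaller. No dose or clinical rule changes.

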6.0 Statistical methods

Randomization: For the proposed multi-center parallel-arms experimental design with a total of N = 153 patients (approximately 38 per Clinical Center), adaptive allocation will be used to minimize the imbalance among doses (overall and within strata). Adaptive allocation will occur by a web-based system, with a manual backup system, devised by the DCC. Participants will be allocated to treatment arm within strata defined by site and history vs. lack of history of any milk thistle preparation use for greater than 30 days duration at any time in the past (except within the last 30 days prior to screening which is an exclusion criterion). Adaptive allocation will be performed via a web-based system located in a private and secure area of the server being used for the study. The web-based system will query the user for the information required to identify the stratum and other information to enable checks that the correct patient was assigned (e.g., patient ID, sex) and return the next treatment assignment in that stratum to the user.

Descriptive Analyses

Tabular and graphical descriptive statistical methods will be used to characterize the study sample at baseline in terms of demographic profile severity of disease and clinical measures. These results will be presented for each arm of the study. The numbers of subjects who drop out of the study or have incomplete data will be described. Descriptive statistical methods will also be used to summarize available measures of compliance recorded during the study by dose level.

6.1 Safety Analysis

To address the primary objective 1 (Section 2.1), adverse events will be tabulated and summarized by descriptive methods for each arm of the study. Estimates of the toxicity rate for each dose level of silymarin (θ_{420} , θ_{700}) and for placebo (θ_o) will be tabulated along with their 95% confidence intervals.

In safety analyses, the toxicity rates of the three arms of the study will be compared. A test of the null hypothesis H_{o2} : " $\theta_o = \theta_{420} = \theta_{700}$ " is not anticipated to be adequately powered due to an

anticipated low toxicity rate and findings from the Phase I study, so it is not a primary hypothesis of this phase II study. An idea of the statistical power afforded by the study to test H_{o2} can be obtained by considering the simplified scenario in which stopping rules for toxicity are not used, and a chi-square test is used to test H_{o2} . In the absence of silymarin, the background rate (θ_o) during the treatment period may be as high as 0.05 (θ_o = 0.05). The maximum tolerated rate is $\theta_{max} = 0.10$. If both of the toxicity rates for the silymarin arms are 0.10, then there is only a 12% chance that data will be collected which yields rejection of H_{o2} at α =0.05.

6.2 Efficacy analysis

To address the primary objective 2, for each arm of the study, an estimate of the response rate π will be tabulated along with a corresponding 95% confidence interval. Point and interval estimates of mean change in log₁₀ (ALT) (a normalizing transformation) will also be tabulated.

The primary null hypothesis, H_{o1} : $\pi_o = \pi_{420} = \pi_{700}$, will be tested against the general alternative hypothesis, H_{a1} that response differs in at least one treatment arm via a chi-square test for association with $\alpha = 0.05$. If H_{o1} is rejected, then pair wise comparisons of the arms will be examined using a sequentially rejective test procedure (Holm, 1979).

Computation of these results for the intent to treat (ITT) analysis will comprise the main results of this study. Similar results will also be examined for the compliant-per-protocol subgroup of participants, defined as patients taking at least 80% of the medication.

Secondary analyses of efficacy will include model-based analyses of the relationship between dose and change in $log_{10}(ALT)$. Appropriate statistical models will be used in which change in $log_{10}(ALT)$ is the dependent variable. Study personnel will also perform analyses designed to aid interpretation of the main results or designed to be exploratory for purposes of hypothesis generation. For example, study personnel will use logistic regression models to investigate the relationship of pharmacokinetic exposure to treatment response.

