6.3 Power considerations

The treatment success rate for each dose level of silymarin (π_{420} , π_{700}) is to be compared to that of placebo (π_0), where the success is defined as the normalization of ALT (≤ 45 IU/L) or a 50% decline to less than 65 IU/L. The primary null hypothesis of interest is H_{o1} : $\pi_0 = \pi_{420} = \pi_{700}$.

In the absence of silymarin, it is anticipated that the background rate (π_0) of spontaneous ALT normalization during a 24-week period may be as high as 0.15 (π_0 = 0.15). A clinically significant success rate would be in the neighborhood 0.40. An approximate idea of the statistical power afforded by the study to test H₀₁ can be obtained by considering the idealized scenario in which toxicity is not a concern, stopping rules for toxicity are not used, and a chi-square test is used to test H₀₁. Assuming that there is no dose response relationship (i.e. $\pi_{420} = \pi_{700}$) and 40% success in each treatment arm with 153 patients (51 per arm) will provide 80% power to reject the null hypothesis at α =0.05 using a chi-square test. On the other hand, if there is a dose response relationship and it is assumed that the probabilities of success are 0.15, 0.30, and 0.50 respectively for placebo, 420mg and 700mg, then with 51 patients in each group, at α =0.05 will provide 94% power to reject the null hypothesis. For participants who drop out, the last observation carried forward method will be used to impute the final outcome so that the last

available ALT would be used to determine the treatment success. Therefore, no overrecruitment to account for loss to follow-up is necessary.

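### With three arms, the overall chi-square test already protects the pairwise comparisons, so the added Holm step is valid but costs power for each dose against placebo

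*Protocol*

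**What the plan says.** Section 6.2 makes equality of the three response rates (placebo, 420 mg, 700 mg) the primary null hypothesis, H_o1. It "will be tested against the general alternative hypothesis" by a chi-square test at 0.05. Only if H_o1 is rejected does the plan continue: "then pair wise comparisons of the arms will be examined using a sequentially rejective test procedure (Holm, 1979". The size of the Holm family is not written out, but the arms are three and no pair is excluded. The natural reading is therefore three pairs, with thresholds 0.05/3 = 0.0167, 0.05/2 = 0.025 and 0.05.

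Section 6.3 opens with the comparisons of interest: "The treatment success rate for each dose level of silymarin" "is to be compared to that of placebo". It then gives power for H_o1 only. At 0.15/0.40/0.40 it says that "40% success in each treatment arm with 153 patients (51 per arm) will provide 80% power to reject the null hypothesis". At 0.15/0.30/0.50 with the same arm size it "will provide 94% power to reject the null hypothesis". The section gives no power for either dose against placebo.

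**The concern.** The plan corrects for multiplicity twice. The overall test acts as a gate at 0.05, and Holm then lowers the thresholds again for the pairs behind the gate. With three arms the gate alone is enough, so the second correction protects nothing further at the nominal level and takes power from the comparisons that section 6.3 names as the aim.

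At stake is how often the trial can say which dose beats placebo, and whether both do. The overall test answers only whether some arm differs, so conclusions on a dose rest on this follow-up step.

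**Working it through.** **Inputs.** From sections 6.2 and 6.3: alpha 0.05; 51 per arm; scenario A 0.15/0.40/0.40; scenario B 0.15/0.30/0.50 (placebo/420 mg/700 mg).

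**1. The plan's own figures.** Noncentral chi-square with 2 df, λ = n Σ(p_i − p̄)² / [p̄(1 − p̄)]. In both scenarios p̄ = 0.95/3 = 0.3167 and p̄(1 − p̄) = 0.2164.
- A: Σ(p_i − p̄)² = 0.04167; λ = 51 × 0.04167 / 0.2164 = 9.82; power 80.8% (stated 80%).
- B: Σ(p_i − p̄)² = 0.06167; λ = 51 × 0.06167 / 0.2164 = 14.53; power 93.7% (stated 94%).

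Both reproduce.

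**2. Why the gate is enough.** The pairwise nulls are π_0 = π_420, π_0 = π_700 and π_420 = π_700. If any two hold, all three rates are equal, so every intersection of two or three of them is H_o1. Closed testing allows a pairwise null to be rejected at 0.05 when it and every intersection containing it are rejected at 0.05. The only such intersection is H_o1, which the gate has tested. This argument needs exactly three arms; it fails with four or more.

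All Holm thresholds are at most 0.05, so every rejection under the plan as written is also a rejection under the closed test. The closed test can only gain.

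**3. Exact power.** All 52³ outcomes of three binomials of size 51 were enumerated, with Pearson chi-square tests without continuity correction.

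| Scenario and claim | Gate + Holm, 3 pairs | Gate + 0.05 per pair | Difference (points) |
|---|---|---|---|
| A: each dose v placebo | 71.8% | 78.0% | 6.2 |
| A: both doses | 60.3% | 71.2% | about 11 |
| A: at least one dose | 83.3% | 84.8% | 1.5 |
| B: 420 mg v placebo | 37.2% | 44.6% | 7.4 |
| B: 700 mg v placebo | 93.7% | 94.7% | 1.0 |
| B: at least one dose | 93.9% | 94.8% | about 1 |

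Exact power of the overall test is 84.8% (A) and 94.9% (B), above the approximation in step 1. The losses are therefore compared only within the exact method.

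**4. Exact error of the closed test.** Family-wise error over all three pairs was 4.7% to 5.4% in seven null and partial-null settings (gate + Holm: 3.3% to 4.9%). The 5.4% is for 420 mg v 700 mg at 0.15/0.40/0.40, against 3.4% as written. At 0.15/0.50/0.50 that comparison reaches 5.9%, against 5.1% as written. The excess comes from the chi-square approximation to discrete data. For placebo comparisons, a false claim for 420 mg occurs in 4.7% at 0.15/0.15/0.40, and any false placebo claim in 4.0% to 4.2% under the overall null (common rate 0.15 or 0.40).

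**The case against.** **The plan is valid.** An overall test followed by Holm controls family-wise error, and a simple conservative follow-up is a legitimate choice. This stands: the point concerns efficiency and there is no error-rate problem.

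**The loss is small where it may matter most.** If the question is whether silymarin works at some dose, Holm costs only 1 to 1.5 points. This also stands. The low power for 420 mg in scenario B comes mainly from 51 per arm at 0.15 v 0.30; the closed test still gives only 45%.

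**Holm may be meant for the two placebo pairs only.** Section 6.3 names only those, and an SAP, which was not available here, could define the family. The loss then nearly vanishes in the protocol's scenarios: 77.8% v 78.0% per dose in A, and 44.5% v 44.6% for 420 mg in B. But section 6.2 speaks of the arms without that limit. If only 700 mg works (0.15/0.15/0.40, an assumption outside the protocol), the narrower reading still gives 73.4% v 79.7%.

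**Stronger readings that the protocol does not support.**
- A reader might infer that 80% and 94% are wrong, or are offered as the chance of success for each dose. Section 6.3 gives them as power for H_o1, and both reproduce.
- A reader might infer that the trial will often reject H_o1 and yet find no dose better than placebo. That happens in 14.2% of trials as written at 0.15/0.15/0.40 (about 5.8% under the closed test), but the protocol does not assume that scenario. In its own two the figure is 1.6% (A) and 1.1% (B).
- A reader might infer that the closed test never exceeds 5%. That holds nominally; exact values reach 5.9%.

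**Conclusion.** The Holm step in section 6.2 is redundant after the overall test. Testing each pair at 0.05 behind the gate is uniformly more powerful at the same nominal family-wise error. Under the protocol's assumptions the gain is about 6 points per dose and 11 points for both doses with equal effects, and about 7 points for 420 mg under dose response. It is about 1 point for 700 mg under dose response, and 1 to 1.5 points for at least one dose.

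This rests on exactly three arms of 51, uncorrected Pearson tests, the protocol's response rates, and Holm over three pairs. It is a worthwhile improvement to the testing rule. The stated power needs no correction; what section 6.3 lacks is power for the dose-against-placebo comparisons with which it opens.

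**What to change.** In section 6.2, replace the Holm sentence with: *If H_o1 is rejected at 0.05, each dose is compared with placebo at 0.05 (closed testing procedure for three arms).* Say whether 420 mg v 700 mg is tested the same way or is descriptive. The descriptive option avoids the comparison in which the exact error reached 5.4% and 5.9%.

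Optionally, in section 6.3, keep 80% and 94% as they are and add the power of each placebo comparison under the new rule: about 78% for each dose under equal effects, and about 45% for 420 mg and 95% for 700 mg under dose response.

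The cost is a wording change, to be made before treatment codes are opened. It needs no patients and keeps the nominal error rate, although realised error moves closer to 5%, or slightly above it for 420 mg v 700 mg if that pair is tested.
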